7.2.3 Study Procedures

1) Visit 1 – Screening/ Baseline visit

The following screening procedures should be completed prior to any study procedure:

- The subject must be given enough time to review and sign the ICF;

- Collection of demographic information (e.g. date of birth, gender, ethnic origin, etc.);
- Review and collection of medical/surgical history;
- Urine/blood pregnancy test: The result of the examination completed within 7 days prior to the signing of ICF is acceptable. If multiple examinations are completed, the result of the examination closest to the time of operation shall prevail;
- Fasting plasma glucose test: The result of the examination completed within 7 days prior to the signing of ICF is acceptable. If multiple examinations are completed, the result of the examination closest to the time of operation shall prevail;
- Review/collection of inclusion/exclusion criteria, and determining whether the subject meets the criteria or not;
- Physical examination: Including body height, body weight, physical examination results of the head and neck, and other contents;
- Concomitant medications: Medications started within 7 days prior to the signing of ICF or currently used
- EQ-5D-5L。

a. Screening

Subjects will be consented prior to any study-specific screening procedures being conducted. Subjects will be considered enrolled into the study upon satisfaction of the following criteria:

- Completion of the informed consent process;
- It is determined by the investigator that the subject meets all inclusion criteria and does not meet any exclusion criteria (Section 7.1.5). The verification must be conducted by the Principal Investigator (PI) and/or authorized investigators prior to randomization.

b. Screen Failures

Subjects who signed the ICF and were screened but not successfully randomized will be considered screen failures. For subjects who are determined to be screen failures, only the following data will be collected:

- Informed consent date;
- Demographic information (age, race, gender, and ethnicity);
- Reason for screening failure.

2) Visit 2 -Randomization

The following information must be obtained during randomization:

- Confirmation of inclusion / exclusion criteria;
- Update of medical/surgical history (prior to randomization);
- Randomization: Central randomization prior to the surgical procedure;
- Concomitant medications;
- Adverse event (AE) (collected since randomization).

Randomization will occur if the patient meets all inclusion criteria and does not meet any exclusion criteria.

The central randomization system will be used in this study, so that subjects will not know their treatment group allocation. Each subject will be randomized to one of the three treatment groups according to the allocation ratio of 1:1:1, and the only difference between the investigational groups and control group lies in the suture material. Each group will include approximately 167 subjects.

3) Visit 3-Surgery

The following information must be obtained during the surgical procedure:

- Surgical data, including:

- Use: Including the code and quantity of study product used, and tissue layer at which the study product is used;
- Suturing time: It is defined as the time required from the first needle insertion for stitching ribbon muscles to the completion of intradermal suture (min);
- Length of operation: It is defined as the time from the incision of skin to the closure of skin (min);
- Total operating room time: It is defined as the time from the start of anesthesia on the subject to the time of leaving the operating room (min);
- Intraoperative suture performance indicators (using VAS scale, see Annex 4-2, collected data of the second case using ██████████ and ██████████ from each Investigator): Ease to pass through tissues, surgical operation profile (including surgical handfeel), suture memory, and wear resistance of suture;
- Concomitant medications: Excluded intraoperative medications for anesthesia;
- Concomitant treatment;
- AEs;
- Product complaints.

Surgical procedures

a. Open thyroid surgical procedure via the anterior cervical curved incision (Kocher's incision):

It is recommended that, the surgery, including the incision closure procedure be performed by not more than three groups of surgeons in each study site, to minimize bias and variation. Open thyroid surgery should be performed according to the diagnosis and treatment practice or specific guidelines of each institution. As required by the expert consensus, the method to make an anterior cervical curved incision (Kocher's incision): Make a collar-like, curved incision about 1-2 cm above the suprasternal notch along a pre-existing skin crease, and parallel to the skin crease. Pay attention to avoiding incision unparallel to local skin grease and subsequently formed a cross. After surgical healing, the incision should be hidden by skin crease of the neck and hence covert. It should be noted that, when making an anterior cervical transverse curved incision, the cervical incision should be made as symmetrical as possible according to the principles of human body aesthetics, to avoid deviation and inclination, disproportion or poor arc of the incision.

The postoperative drainage tube (if any) should be placed in another incision made, other than the incision above, and cannot be placed in full length of the incision.

b. Incision closure procedure using study products:

All the subjects must have their incision closed sutures according to the treatment group to which they are assigned. The specific suture materials and methods are as follows:

Investigational group 1: Use the study device ██████████ for continuous suture of the ribbon muscles, ██████████ for interrupted suture of the platysma, and ██████████ for continuous subcuticular suture;

Investigational group 1			
Level	Suture Material	Suture Technique	Product Code
Ribbon muscles	██████████	Continuous	██████████
Platysma	██████████	Interrupted	██████████
Intradermal	██████████	Continuous	██████████

Investigational group 2: Use ██████████) for continuous suture of the ribbon muscles, ██████████) for interrupted suture of the platysma, and the study device ██████████) for continuous subcuticular suture;

Investigational group 2			
Level	Suture Material	Suture Technique	Product Code
Ribbon muscles	██████████	Continuous	██████████
Platysma	██████████	Interrupted	██████████
Intradermal	██████████	Continuous	██████████

Control group: Use the control device ██████████) for continuous suture of the ribbon muscles, ██████████) for interrupted suture of the platysma, and the control device ██████████) continuous subcuticular suture.

Control group			
Level	Suture Material	Suture Technique	Product Code
Ribbon muscles	██████████	Continuous	██████████
Platysma	██████████	Interrupted	██████████
Intradermal	██████████	Continuous	██████████

None study product should be used once incision closure, despite of any reason leading to original sutures removal, incisions re-opening or re-suturing.

The method of use of the investigational devices is as follows:

1. Secure the fixation loop portion to robust tissue by taking a bite in the designated tissue, passing the needle through the loop and pulling tautly around the anchoring tissue.
2. After the device is anchored into the tissue, grasp the strand and approximate tissue to the desired tension. Bites, or passes through the tissue, can be taken in a continuous suturing technique to approximate the wound. Care should be taken to utilize the device on the barbed segments only. Do not attempt to approximate wounds using the non-barbed segment near the needle, as the barbs are required for successful wound approximation with the device.
3. (1) To complete the closure in subcuticular closure, take at least one pass in the reverse direction. Then pass the needle across the incision and take a split thickness bite perpendicular to the incision and exit the skin.
(2) To complete the closure in all other tissue layers, take at least two passes in the reverse direction to complete the closure
4. Then gently pull on the free end of the device and cut flush with the surface of the tissue.
To remove the entire device: Cut the device at the end anchored with the loop, and then pull the distal end to remove the device.

Other sutures used in the trial should be used as per surgical procedure. Do not use skin adhesive at the incision site after the suture is done.

Postoperative care:

Postoperative care should be given according to the routine practice of the study site or the

specific requirements of postoperative care guidelines. The subjects' condition should be closely monitored until they are discharged.

4) Visit 4 – Day 5-7 post-surgery

The following information must be obtained at this visit:

- Concomitant medications;
- Concomitant treatment;
- Imaging data of incision: 1 picture of complete neck anterior view containing full length of the incision;
- Wound healing grade assessment: Assessed by Central Imaging evaluators according to the imaging data;
- Postoperative incision pain score;
- EQ-5D-5L;
- Incision SSI, and ASEPSIS score assessed in subjects with confirmed SSI;
- Wound complication assessment, including: incisional wound separation or incisional wound dehiscence requiring intervention, delayed incisional wound healing, etc.;
- Discharge date;
- AEs;
- Product complaints.

5) Visit 5 – Day 28-35 post-surgery

The following information must be obtained at this visit:

- Concomitant medications;
- Concomitant treatment;
- Imaging data of incision: Collect 5 pictures of incision (including a picture of complete neck anterior view containing full length of the incision, a picture taken parallel to the incision plane, a picture taken at a 45° angle to incision plane, and incision lateral view pictures of both sides (one for each));
- Modified Hollander Wound Evaluation Scale;
- Postoperative incision pain score;
- EQ-5D-5L;
- Incision SSI, and ASEPSIS score assessed in -subjects with confirmed SSI;
- Wound complication assessment, including: incisional wound separation or incisional wound dehiscence requiring intervention, delayed incisional wound healing, etc.;
- AEs;
- Product complaints.

6) Withdraw visit – For subjects randomized but without any of study sutures used and for subjects who withdraw ICF

For subjects who are randomized but without any of study sutures used for incision closure, this visit is conducted as early as possible. For subjects who withdraw ICF, this visit is conducted as early as possible with subjects' permission. Telephone visit is acceptable. The following information must be obtained at this visit: AEs; Product complaints.

7.3 Monitoring Plan

This study is performed according to the Good Clinical Practice for Medical Device Trials and related laws and regulations, such as ISO 14155, the Declaration of Helsinki.

The Sponsor takes the monitoring responsibility for the clinical trial and will select the qualified monitor to execute the monitoring responsibility.

The monitor should comply with the related laws and regulations and the standard operating procedure (SOP) established by the Sponsor to monitor each study phase.

The monitor should contact and visit the investigators at a regular basis and make the on-site visit/monitoring during the study. The monitor should visit each site right after the first subject is enrolled, and regular site visits during the duration of the study.

The monitoring will include visits to the clinical trial institution, verification of source data, communication with investigators and clinical trial institution, ensuring that this study will be performed strictly in compliance with the protocol and the requirements of regulations and Good Clinical Practice, etc.

The on-site monitoring includes verifying the source document and checking whether source data is true, accurate, complete and clear, the original document of each subject is complete.

This study might be audited by the Sponsor or inspected by Regulatory Authority. If such audit/inspection is performed, the Investigator and the site must agree the auditor to look up the records of subjects. The Investigator agrees the Sponsor or its appointed representative and Regulatory Authority to monitor all project-related study documents on site by signing on the signature page of this trial protocol.

See the Monitoring Plan for details.

8 Statistical Considerations

8.1 Statistical Design, Method and Analysis Procedure

This study is a multicenter, prospective, randomized controlled study to evaluate the of ██████████ and ██████████ used in thyroid surgery to suture surgical incision. Prior to surgery subjects will be randomized to the investigational group 1 (██████████), investigational group 2 (██████████) or the control group according to the allocation ratio of 1:1:1. The primary **efficacy** endpoint is the proportion of subjects achieving Grade A wound healing (success) of surgical incision in each group. A blind assessment will be performed on the wound healing status by independent Central Imaging evaluators on Day 5-7 post-surgery using the imaging data (a picture of complete neck anterior view, covering full length of the incision).

This is a non-inferiority trial with two treatment group comparisons, investigational group 1 versus control group, and investigational group 2 versus control group. The overall family-wise error rate is controlled at 0.025 level using the Holm's multiple comparisons procedure. The expected success rate is 98% for all the three groups.

For each of the two comparisons, the statistical hypotheses for testing the non-inferiority of the investigational group to control is presented as follows:

- $H_0: P_T - P_C \leq -0.05$ tested against the alternative hypothesis
- $H_a: P_T - P_C > -0.05$

P_C is the proportion of successes (Grade A healing) in the control group and P_T is the proportion of successes in each of the investigational groups (1 and 2).

The proportion of subjects with Grade A healing will be summarized for each treatment group and will be calculated as the number of subjects with Grade A healing divided by the total number of subjects randomized to that treatment who had the surgical wound closed using the randomized suture. Within-treatment group, two-sided 95% confidence intervals for the proportions of successes will be provided using the Clopper-Pearson method.

For the primary endpoint analysis, the Holm's step-down procedure will be used. For each of

the two group comparisons, the p-value associated with the non-inferiority test will be calculated using the Normal approximation Z (pooled) statistic. If the smaller p-value is smaller than 0.0125, then the null hypothesis associated with this p-value will be rejected and it will be concluded that the associated Test product is non-inferior to Control; subsequently, the larger p-value will be compared to 0.025 in order to test the non-inferiority of the other Test product to Control. If the smaller p-value is larger than 0.0125, then neither of the null hypotheses can be rejected and it will be concluded that, for both investigational devices, the study failed to demonstrate non-inferiority to Control.

The primary endpoint will be analyzed using the Full Analysis Set (FAS) and Per-Protocol (PP) sets. The PP analysis will be considered the primary analysis, while the FAS analysis will be considered supportive. The analysis sets for this study are defined in section 8.8.

The following **secondary efficacy endpoints** will be summarized descriptively by treatment group for the FAS:

1. Incision suturing time, defined as the time required from the first needle insertion for stitching ribbon muscles to the completion of intradermal suture (min);
2. Modified Hollander Wound Evaluation Scale;
3. Postoperative incision pain score (VAS Scale);
4. Health related quality of life scale (EQ-5D-5L).

In addition, the following safety endpoints will be summarized descriptively t by treatment group for the Safety analysis set:

1. Incidence of postoperative SSI;
2. ASEPIS score (only assessed in subjects with confirmed SSI);
3. Incidence of incisional wound separation or wound dehiscence requiring intervention;
4. Incidence of delayed incisional wound healing events;
5. Incidence of other AEs;
6. Product complaints.

The incidence of AEs will be assessed according to the classification of event and summarized descriptively by treatment groups. Incidence of AEs will also be assessed by onset time (intraoperative or postoperative), relationship to study surgical procedure, relationship to the study product, severity, and seriousness.

All continuous variables will be summarized by number of subjects, mean, standard deviation, median, minimum and maximum. All categorical data will be summarized by frequencies and associated percentages. No inferential statistics will be generated for secondary efficacy and safety endpoints.

8.3 Significance Level and Power of Clinical Trial

Determination of the sample size was performed assuming 80% power and a significance level of 0.0125 for each comparison. To control the overall Type I error rate at a 0.025 level for the two hypotheses being tested, Holm's stepdown multiple comparison procedure is being utilized.

8.4 Expected Dropout Rate

The expected dropout rate in this study is 10%.

8.5 Criterion of Acceptability/Unacceptability of Clinical Trial Result

For the primary endpoint analysis, the Holm's step-down procedure will be used. For each of the two group comparisons, the p-value associated with the non-inferiority test will be calculated. If the smaller p-value is smaller than 0.0125, then the null hypothesis associated with this p-value will be rejected and it will be concluded that the associated Test product is non-inferior to Control; subsequently, the larger p-value will be compared to 0.025 in order to test the non-inferiority of the other Test product to Control. If the smaller p-value is larger than 0.0125, then neither of the null hypotheses can be rejected and it will be concluded that, for both test devices, the study failed to demonstrate non-inferiority to Control.

8.6 Criteria and Reason for Terminating the Trial Based on the Statistical Results

No interim analysis and corresponding early termination criteria, are planned for this trial; therefore this section does not apply. All the statistical analyses will be done after all the data are collected, and after study database lock. A Statistical Analysis Plan will be finalized prior to database lock and the performing of any final analyses.

8.7 Statistical Method of All Data, together with the Handling Method of Missing, Unused and Error Data (including Termination and Withdrawal Halfway) and Unreasonable Data

All study endpoints will be analyzed using the available data. There will be no missing data imputation in this study.

8.8 Selection Criteria and Reason of Subjects Included in the Analysis

All subjects that meet the inclusion/exclusion criteria are considered to meet the requirements for recruitment.

Three analysis sets in the study are defined for this study, as follows:

- FAS consists of all the enrolled subjects who were randomized and for whom the randomized suture materials were used for incision closure.
- PP (evaluable) Set contains all the subjects in the FAS who have no major protocol

deviation, have data available for primary efficacy endpoint and do not meet any of the following criteria:

- Subject undergoes any of the following procedures, in addition to thyroidectomy:
 - 1、 Any surgical procedure which require additional neck incisions or extend the original incision;
 - 2、 Cervical lymph node dissection (except the dissection of lymph nodes in the VI area);
 - 3、 Other unplanned surgical procedures (except the procedure that the investigator doesn't think it will affect the original incision's healing)
- Subject's intraoperative frozen pathology or postoperative paraffin section pathology suggests anaplastic thyroid cancer;
- Subject receives any surgical procedures that lead to re-opening of the cervical incision during the period from the wound closure to the completion of study, except for surgeries related to surgical incision complication or study device.
- Safety Set contains all the enrolled subjects who receive surgery.

Major protocol deviations are deviations that have an impact on the primary endpoint assessment or randomization. These will be determined prior to database lock.

The analysis of primary efficacy endpoint will be performed using FAS and PP Sets. However, while the primary analysis is based on the PP Set, FAS analysis will only be used as supplemental analysis.

The secondary efficacy endpoints will be analyzed using the FAS, while the safety endpoints will be analyzed using the Safety Set.

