7.1.3 Measures to Reduce and Avoid Bias

In the study, central randomization will be adopted to randomly assign eligible subjects to one of the three groups: investigational group 1, investigational group 2 or control group according to the same inclusion/exclusion criteria to reduce the impact caused by unknown confounding factors and avoid selection bias.

Study blinding is as follows:

- Subject: Subjects are informed prior to surgery that they will be randomized to any of the study groups with equal probability, and during the surgery, a blinding method will be adopted for them.
- Investigator responsible for incision suture: Considering the investigational groups and

[PROTOCOL VERISON AND DATE] V2.0/2019-09-30

control group use different shapes and usages of suture, it is impossible to blind investigators who are responsible for suturing.

- Central evaluator: Imaging data will be submitted to Imaging Center for assessment to assess the primary endpoint and the modified Hollander score among secondary endpoints. The Central Imaging evaluators will be blinded.
- Monitor: As the product information is specified on the detachable label supplied with the product and instrument counting and source document verification is - done with the study product inventory records and subject's medical record, the monitor will not be blinded.

In addition, this study will collect data about objective measures, study related information will be recorded in the source medical records as detailed as possible, the monitor will pay attention to verifying the data in the source medical records during the monitoring process, investigator training will be strengthened, and investigators will closely communicate with subjects to improve compliance of subjects. This will help to reduce the informational bias.

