7.1.5 Subject Selection

1) Inclusion criteria

1. The subject is ≥ 18 , and < 70 years old
2. Planned open thyroid surgery, adopting an anterior cervical curved incision (Kocher's incision);
3. Subject who volunteers to participate in this study, follows the study requirements and follow-up visit and signs the written Informed Consent Form voluntarily;
4. Subject who agrees to not schedule any elective surgical operation except the study surgery before the study is completed;
5. The investigator considers the subject's expected postoperative survival time is not less than 3 months.

2) Exclusion Criteria

1. Female subjects who are pregnant or lactation at screening;
2. Preoperative clinical staging shows stage IV thyroid cancer, or cervical lymph nodes dissection is planned;
3. Suspected or confirmed anaplastic thyroid cancer;
4. Peripheral vascular disease affecting blood supply of the neck;
5. Active infectious collagenosis (e.g. scleroderma), or any other disease that would interfere with the wound closure;
6. Fasting plasma glucose (FPG) ≥ 7.7 mmol/L;
7. History of coagulation diseases;
8. Current oral or intravenous antibiotic therapy for existing disease or infection;
9. History of immunosuppressant use (e.g. steroids) within the last 6 months;
10. Chemotherapy or radiotherapy within the last 6 months, or planned chemotherapy or radiotherapy during the study;
11. Personal or family history of keloid formation or hyperplasia;
12. Current participation in any other drug (within 30 days or within 5 half-lives of the investigational drug) or device clinical study;
13. History of any thyroid surgery, except thyroid fine-needle aspiration biopsy;
14. Planned use of skin adhesive at the incision site;
15. The subject is not suitable for participating in this study for any other reasons, as judged by the investigator.

3) Criteria and procedure of Study Discontinuation

The criteria for Subject's Discontinuation from Study include, but are not limited to:

1. Withdrawal of consent: Subject decides to withdraw from the study. This decision must be "self-determination" and should be documented;
2. Investigator's judgement: The Investigator may determine the withdrawal of subjects from the study according to reasonable medical judgement and such withdrawal may benefit the subject mostly.

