3. Adverse event (AE)/Serious Adverse event (SAE: The AE or SAE may not cause the subjects to discontinue the study treatment. If the investigator decides to withdraw a subject from the study, this subject must be followed up, until the AE/SAE is resolved or until the stable clinical endpoint is reached;

4. Subject died;
5. Lost to follow-up: All subjects should be able to participate in all scheduled visits, providing the appropriate contact information. If a subject can't return to undergo the scheduled clinical visit, attempts to contact the subject by phone should be done 3 times to ask the subject to participate in all scheduled visits. Each attempt to contact should be recorded in the source document. If the subject fails to respond to all three telephone contact attempts, the Investigator must send a registered mail or Express Mail Service (EMS) . If the subject fails to respond to the registered mail or EMS and makes no further contact, the subject is considered lost-follow-up and the eCRF at the end of study must be completed;
6. The Sponsor discontinues the study;
7. The health regulatory agency requests discontinuation of the study.

Procedure for subject's discontinuation from the trial:

Subjects should stay in this study until the 28-35day follow-up visit defined in the study protocol is completed. If a subject withdraws from this study prematurely, the reason for withdrawal must be recorded in the source record and the investigational study file will be submitted via e-CRF.

Subjects who are withdrawn from the study early will be included in the analysis of results; however, no new subjects will be recruited to replace the subjects withdrawn from the study.

Criteria of Sponsor's Discontinuation of the Trial:

The Sponsor has the right to terminate the study early for a single site, multiple sites or all sites temporarily or permanently. Reasons may include but are not limited to: safety issue or ethical issue, inaccurate or incomplete data record, non-compliance or dissatisfactory quality of the study recruitment.

Flow of Sponsor's Discontinuation of the Trial:

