7.1.6 Efficacy Evaluation Method

1) Description of efficacy parameters

The primary efficacy endpoint is defined as the proportion of subjects achieving Grade A healing (success) of surgical incision in each group.

According to clinical routine practice, wound healing status should be assessed during removal of stitches of incision and generally, stitches at the incision of head, face and neck are taken out on Day 4-5 post-surgery; however, if energy devices are used (e.g. electrotome), the removal of stitches should be delayed by 1-2 days. In this study, all the skin layers can be performed with intradermal continuous suture using absorbable sutures, thus it is unnecessary to take out stitches at the incision. Therefore, the time of wound healing assessment in this study is set as Day 5-7 post-surgery.

Wound healing status is classified into three grades:

- Grade A healing: Good healing with no adverse reaction;
- Grade B healing: Inflammatory reaction(s) at the healing, such as red swelling, induration, hematoma, effusion, etc., but without suppuration;
- Grade C healing: Suppuration of incision, requiring incision and drainage and other treatments.

Secondary Efficacy Endpoints include:

1. Incision suturing time, defined as the time required from the first needle insertion for stitching ribbon muscles to the completion of intradermal suture (min);
2. Modified Hollander Wound Evaluation Scale (see Annex 3), assessed by Imaging Center evaluators using pictures, including: a picture of complete neck anterior view containing full length of the incision, a picture taken parallel to the incision plane, a picture taken at a 45° angle to the incision plane, and incision lateral view pictures of both sides (one for each);
3. Postoperative incision pain score (VAS scale, see Annex 4-1);
4. Health related quality of life scale (EQ-5D-5L): Subjects are required to select the most appropriate levels in 5 aspects to determine their health status (see Annex 5):
 - Motility
 - Self care
 - Daily activities
 - Pain/discomfort
 - Anxiety/depression

2) Selection of method and time to evaluate, record and analyze the efficacy parameters

The primary efficacy endpoint (wound healing grade) will be assessed by independent, blinded Imaging Center according to the picture (a picture of complete neck anterior view, containing full length of the incision) on Day 5-7 post-surgery and documented in the e-CRF.

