## 4. PLANNED ANALYSES

## 5. ANALYSIS SETS

Agreement and authorization of subjects included/excluded from each analysis set will be conducted prior to the unblinding of the study.

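### The re-opening exclusion in the primary PP set runs to study completion, past the Day 5-7 photograph that fixes the outcome, so a later re-opening judged unrelated removes a valid recorded result

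*Protocol*

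**What the plan says.** **Exclusion.** Protocol 8.8 lists among the PP exclusions: "Subject receives any surgical procedures that lead to re-opening of the cervical incision". The window for this event, and its exception, are given as "during the period from the wound closure to the completion of study, except for surgeries related to surgical incision complication or study device". SAP 5.2 repeats the rule with the same window. Re-openings for an incision complication or the device are therefore kept; only those judged unrelated lead to exclusion.

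**Outcome.** Protocol 7.1.6 ties the assessment to one visit: "Therefore, the time of wound healing assessment in this study is set as Day 5-7 post-surgery". Blinded central evaluators grade a single photograph from that visit (V4).

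**End of study.** Protocol 7.1.5: "Subjects should stay in this study until the 28-35day follow-up visit defined in the study protocol is completed".

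**Role of PP.** Protocol 8.1: "The PP analysis will be considered the primary analysis, while the FAS analysis will be considered supportive". Under Protocol 8.8, secondary efficacy endpoints use the FAS and safety endpoints use the Safety Set, so PP serves the primary endpoint alone.

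**Neighbouring criterion.** The first PP exclusion in both documents covers procedures in addition to thyroidectomy: extra or extended neck incisions, neck node dissection outside area VI, and other unplanned surgery unless the investigator thinks that healing is unaffected. It states no time limit.

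**The concern.** Take a subject closed with the assigned suture and photographed on Day 6, whose incision is re-opened on Day 15 for a reason judged unrelated to an incision complication or the device. The photograph already exists and the re-opening cannot alter what it shows. The subject nevertheless leaves the deciding analysis, so membership of the primary set is conditioned on an event after the outcome.

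The exclusion also turns on a relatedness judgement. Neither document says who makes it or that this person is blinded. Protocol 7.1.3 says of the operators that "it is impossible to blind investigators who are responsible for suturing", and wound complications are assessed at the V4 visit (Protocol 7.2.3). At an expected success rate of 98% there are very few failures, so the result is sensitive to losing even one. Losing a test-arm failure favours non-inferiority; losing a control-arm failure works against it.

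**Working it through.** **1. The plan's own figure.** Inputs from Protocol 8.2.1 and SAP 13.1.1: success 0.98 in both arms, margin 0.05, one-sided 0.0125, power 80%, dropout 10%.

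n = (2.2414 + 0.8416)² × 2 × 0.98 × 0.02 / 0.05² = 9.505 × 0.0392 / 0.0025 = 149.04, so 150 per arm (power 80.3%). Enrolment: 150 / 0.90 = 166.7, so 167 per arm and 501 in total. The plan's figures reproduce.

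**2. Does the late window serve any analysis?**

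| Item | Place | Timing or set |
|---|---|---|
| Primary outcome | Protocol 7.1.6 | Day 5-7 photograph |
| Re-opening exclusion | Protocol 8.8, SAP 5.2 | Closure to study completion (Day 28-35) |
| Day 28-35 endpoints, such as the Hollander scale | Protocol 7.2.1, 8.8 | Analysed in FAS, not PP |
| Major deviation | Protocol 8.8 | Must affect the primary assessment or randomization |

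A re-opening after the photograph affects neither the primary assessment nor randomization, and no endpoint measured later is analysed in PP. The late part of the window therefore departs from the section's own principle and protects nothing. It makes up between 21/28 = 75% (Day 7 to 28) and 30/35 = 86% (Day 5 to 35) of the window. That is calendar time, not a share of re-openings.

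**3. What one deletion does.** Expected failures per arm: 150 × 0.02 = 3. The planned pooled test is Z = (pT − pC + 0.05) / √[p̄(1 − p̄)(1/nT + 1/nC)]. Control is 147/150 throughout.

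- Test 145/150: difference −0.0133, p̄ = 292/300, Z = 0.0367 / 0.0186 = 1.971, p = 0.0244.
- One failure removed, 145/149: difference −0.0068, p̄ = 292/299, Z = 0.0432 / 0.0175 = 2.468, p = 0.0068.
- One Grade A subject removed instead, 144/149: p = 0.0254. The shift is small, although in this borderline example it happens to cross 0.025.
- Test 144/150: p = 0.0639; with two failures removed, 144/148, p = 0.0072.

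**4. Effect under Holm** (Protocol 8.1 and 8.5), for the move from 0.0244 to 0.0068:

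| p of the other comparison | Before deletion | After deletion |
|---|---|---|
| Below 0.0125 | Passes at 0.025 | Passes; no change |
| 0.0125 to 0.025 | Neither device passes | Both pass |
| Above 0.025 | Neither device passes | This device passes |

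**5. How often?** The documents give no re-opening rate. Assume that 1% to 3% of subjects have a late unrelated re-opening: 150 × 0.01 to 0.03 = 1.5 to 4.5, or about 2 to 5 subjects per arm. Nearly all would be Grade A. If re-opening is independent of grade, the expected number of failures lost per arm is 3 × 0.01 to 0.03 = 0.03 to 0.09.

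**The case against.** The case that this matters little is substantial, and most of it stands.

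- The exception keeps re-openings for incision complications or the device, which is the likeliest reason to re-open a failed wound.
- Inclusion criterion 4 restricts further surgery: "Subject who agrees to not schedule any elective surgical operation except the study surgery before the study is completed". This makes late re-openings rarer but does not exclude unplanned ones.
- SAP 5: "Agreement and authorization of subjects included/excluded from each analysis set will be conducted prior to the unblinding of the study". This limits steering when the sets are agreed. It does not blind a relatedness attribution made earlier, nor does it restore a dropped outcome.
- Neither definition of the FAS carries a re-opening exclusion, so a discrepancy between PP and FAS would be visible. The FAS is only supportive, however.
- Each comparison is planned at 80% power for 0.0125. Under the plan's assumptions the other device will usually pass, and the example then changes nothing.
- Changing the re-opening criterion alone would not be enough. The additional-procedures criterion has no time limit and could still exclude the Day 15 subject.

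A reader might infer that unblinded sites can choose which failures to delete. The documents do not support that: they do not say that the site judges relatedness under the re-opening criterion, and they do not say that it knows the central grade. The gap is that no blinded role is assigned.

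**Conclusion.** The point holds, with a limited and unquantified effect. In both documents the re-opening exclusion outlasts the outcome that it is meant to protect. A re-opening after V4 that is judged unrelated takes a valid recorded grade out of the deciding analysis.

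The number of such cases is probably small. The 1% to 3% rate is an assumption, and so is independence between re-opening and grade. The p-values show that one deleted failure can change the conclusion when the other comparison has p above 0.0125; they do not show that this is likely.

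Two further inferences should be resisted. The 75% to 86% figure does not mean that most re-openings fall after the photograph, because the documents give no timing of re-openings. Nor does the rule drop failed wounds in general, because complication- and device-related re-openings stay in PP. Exclusion of re-openings before the photograph is a separate question and is not challenged here. The change is worth making because it costs almost nothing and removes a condition that depends on a post-outcome event.

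**What to change.** In Protocol 8.8 and SAP 5.2:

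1. End the re-opening criterion at the V4 (Day 5-7) photograph instead of at study completion.
2. State that the additional-procedures criterion likewise applies only to procedures performed before the V4 photograph.
3. State that subjects with later procedures stay in PP with their recorded grade, unless another PP criterion excludes them.

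The cost is a short wording change to two criteria in each document, made before database lock. It needs no new data and no change in clinical conduct. The sample size stays at 150 evaluable and 167 enrolled per arm, 501 in total, and the PP set can only stay the same or become slightly larger.
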